- Rollover period defined as first dose in the rollover to last dose in the rollover study + 28 days (Treated Set, patient continuing in the rollover study).

Tables of TEAEs by maximum severity will be prepared using the following rules: each SOC / PT category will include only the AEs with the worst severity for each patient. In the Overall category, all AEs of the patient will be presented. Each patient will be counted only once with the worst severity in each SOC and each PT level as well as in the Overall level.

Number of patients who died will be tabulated.

All AEs/SAEs will be listed. Non-treatment emergent adverse events will be identified accordingly in the listing.

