9.5. Other Safety Measures

eCRF form: “VITAL SIGNS”, “ECG”, “PHYSICAL EXAMINATION”.

Vital signs

Vital signs (respiratory rate (breaths/ minute), pulse rate (beats/ minute), and systolic and diastolic blood pressure (mmHg), and axillary temperature ($^{\circ}\text{C}$)), body weight (kg) and body height (cm) results will be presented in accordance with section 7.

Vital signs results will be presented by visit of assessment as scheduled in the Table 1. Body height will be assessed only at screening.

Vital signs and body weight results will be presented as the following outputs:

- descriptive statistics for measured values and changes from baseline (vital signs, body weight, BMI);
- frequency tables for Out of range: No/Yes clinically significant (Yes CS) / Yes non-clinically significant (Yes NCS) (vital signs).

All data will be listed.

ECG

A 12-lead electrocardiogram (ECG) results will be represented in accordance with section 7 by visit of assessment as scheduled in the Table 1 as the following outputs:

- shift table by post baseline visit compared to baseline for Normal/Abnormal clinically significant (Abnormal CS) / Abnormal non-clinically significant (Abnormal NCS) evaluation for General assessment

ML39355_STATISTICAL ANALYSIS PLAN_Final 2.0_17 June 2020

- descriptive statistics of ECG parameters and their changes from baseline (Heart rate, beats/min; QT interval, ms; QTC-F interval, ms).
- frequency table for Out of range: No/Yes clinically significant (Yes CS) / Yes non-clinically significant (Yes NCS) for ECG parameters.

All ECG data will be listed.

Physical examinations

Complete physical examination is performed at the Screening only (head, eyes, ears, nose, and throat, and the cardiovascular, dermatological, musculoskeletal, respiratory, gastrointestinal, genitourinary, and neurological systems). At subsequent visits, only limited, symptom-directed physical examinations should be performed.

Physical examination results as scheduled in the Table 1 will be presented in accordance with section 7 by visit of assessment as the following output:

- frequency table for Normal/Abnormal clinically significant (Abnormal CS) / Abnormal non-clinically significant (Abnormal NCS) evaluation.

All physical examination data will be listed.

10. Pharmacokinetics

Not Applicable.

11. Other Analyses

Not Applicable.

12. Reporting Conventions

Not Applicable.

13. Technical Details

Statistical analysis will be performed using SAS 9.4.

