- Table 3.3.1 Treatment-emergent adverse events during treatment period (TS)
- Table 3.3.2 Treatment-emergent adverse events during rollover study (TS, patients continuing in the rollover study)
- Table 3.3.3 Treatment-emergent adverse events during whole study period (TS)
- Table 3.4.1 Treatment-emergent adverse events related to the study drug during treatment period (TS)
- Table 3.4.2 Treatment-emergent adverse events related to the study drug during rollover study (TS, patients continuing in the rollover study)

ML39355_STATISTICAL ANALYSIS PLAN_Final 2.0_17 June 2020

Table 3.4.3 Treatment-emergent adverse events related to the study drug during whole study period (TS)

Table 3.5.1 Serious treatment-emergent adverse events during treatment period (TS)

Table 3.5.2 Serious treatment-emergent adverse events during rollover study (TS, patients continuing in the rollover study)

Table 3.5.3 Serious treatment-emergent adverse events during whole study period (TS)

Table 3.6.1 Serious treatment-emergent adverse events related to the study drug during treatment period (TS)

Table 3.6.2 Serious treatment-emergent adverse events related to the study drug during rollover study (TS, patients continuing in the rollover study)

Table 3.6.3 Serious treatment-emergent adverse events related to the study drug during whole study period (TS)

Table 3.7.1 Treatment-emergent adverse events during treatment period by maximum severity (TS)

Table 3.7.2 Treatment-emergent adverse events during rollover study by maximum severity (TS, patients continuing in the rollover study)

Table 3.7.3 Treatment-emergent adverse events during whole study period by maximum severity (TS)

Table 3.8.1 Treatment-emergent adverse events related to the study drug during treatment period by maximum severity (TS)

Table 3.8.2 Treatment-emergent adverse events related to the study drug during rollover study by maximum severity (TS, patients continuing in the rollover study)

Table 3.8.3 Treatment-emergent adverse events related to the study drug during whole study period by maximum severity (TS)

Table 3.9.1 Treatment-emergent adverse events of special interest during treatment period (TS)

Table 3.9.2 Treatment-emergent adverse events of special interest during rollover study (TS, patients continuing in the rollover study)

Table 3.9.3 Treatment-emergent adverse events of special interest during whole study period (TS)

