NCI CTCAE version 4.0 was used for assessing AE severity. AEs are coded using MedDRA version XX.X.

Path to the program code, date and time of output

Data extracted: DD.MM.YYYY

< System organ classes (SOC) and preferred terms (PT) within each SOC should be sorted in descending order of n (%). >

ML39355_STATISTICAL ANALYSIS PLAN_Final 2.0_17 June 2020

Similar to table 3.7.1, the following tables will be constructed (with the corresponding corrections of underlined fragments in the note):

F. Hoffmann-La Roche Ltd
ML39355

Table 3.7.2 Treatment-emergent adverse events during rollover study by maximum severity

Treated set (TS, patients continuing in the rollover study)

Page X of X

F. Hoffmann-La Roche Ltd
ML39355

Table 3.7.3 Treatment-emergent adverse events during whole study period by maximum severity

Treated set (TS)

Page X of X

F. Hoffmann-La Roche Ltd
ML39355

Table 3.8.1 Treatment-emergent adverse events related to the study drug during treatment period by maximum severity

Treated set (TS)

Page X of X

F. Hoffmann-La Roche Ltd
ML39355

Table 3.8.2 Treatment-emergent adverse events related to the study drug during rollover study by maximum severity

Treated set (TS, patients continuing in the rollover study)

Page X of X

F. Hoffmann-La Roche Ltd
ML39355

Table 3.8.3 Treatment-emergent adverse events related to the study drug during whole study period by maximum severity

Treated set (TS)

Page X of X

ML39355_STATISTICAL ANALYSIS PLAN_Final 2.0_17 June 2020

Similar to table 3.3.1, the following tables will be constructed (with the corresponding corrections of underlined fragments in the note):

F. Hoffmann-La Roche Ltd
ML39355

Table 3.9.1 Treatment-emergent adverse events of special interest during treatment period
Treated set (TS)
Page X of X

F. Hoffmann-La Roche Ltd
ML39355

Table 3.9.2 Treatment-emergent adverse events of special interest during rollover study
Treated set (TS, patients continuing in the rollover study)
Page X of X

F. Hoffmann-La Roche Ltd
ML39355

Table 3.9.3 Treatment-emergent adverse events of special interest during whole study period
Treated set (TS)
Page X of X

F. Hoffmann-La Roche Ltd
ML39355

Table 3.10.1 Treatment-emergent adverse events leading to death during treatment period
Treated set (TS)
Page X of X

F. Hoffmann-La Roche Ltd
ML39355

Table 3.10.2 Treatment-emergent adverse events leading to death during rollover study
Treated set (TS, patients continuing in the rollover study)
Page X of X

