F. Hoffmann-La Roche Ltd
ML39355

Table 3.10.3 Treatment-emergent adverse events leading to death during whole study period
Treated set (TS)
Page X of X

F. Hoffmann-La Roche Ltd
ML39355

ML39355_STATISTICAL ANALYSIS PLAN_Final 2.0_17 June 2020

Table 3.11.1 Treatment-emergent adverse events leading to discontinuation of study drug during treatment period

Treated set (TS)

Page X of X

F. Hoffmann-La Roche Ltd

ML39355

Table 3.11.2 Treatment-emergent adverse events leading to discontinuation of study drug during rollover study

Treated set (TS, patients continuing in the rollover study)

Page X of X

F. Hoffmann-La Roche Ltd

ML39355

Table 3.11.3 Treatment-emergent adverse events leading to discontinuation of study drug during whole study period

Treated set (TS)

Page X of X

F. Hoffmann-La Roche Ltd

ML39355

Table 3.12.1 Treatment-emergent adverse events related to the study drug and leading to death during treatment period

Treated set (TS)

Page X of X

F. Hoffmann-La Roche Ltd

ML39355

Table 3.12.2 Treatment-emergent adverse events related to the study drug and leading to death during rollover study

Treated set (TS, patients continuing in the rollover study)

Page X of X

F. Hoffmann-La Roche Ltd

ML39355

Table 3.12.3 Treatment-emergent adverse events related to the study drug and leading to death during whole study period

Treated set (TS)

Page X of X

F. Hoffmann-La Roche Ltd

ML39355

Table 3.13.1 Non-serious treatment-emergent adverse events occurred at a frequency of $\geq 5\%$ during treatment period

Treated set (TS)

Page X of X

F. Hoffmann-La Roche Ltd

ML39355_STATISTICAL ANALYSIS PLAN_Final 2.0_17 June 2020

ML39355

Table 3.13.2 Non-serious treatment-emergent adverse events occurred at a frequency of $\geq 5\%$ during rollover study

Treated set (TS, patients continuing in the rollover study)

Page X of X

F. Hoffmann-La Roche Ltd

ML39355

Table 3.13.3 Non-serious treatment-emergent adverse events occurred at a frequency of $\geq 5\%$ during whole study period

Treated set (TS)

Page X of X

ML39355_STATISTICAL ANALYSIS PLAN_Final 2.0_17 June 2020

Table 3.14 Deaths
Treated set (TS)
Page X of X

	Total (N = XX) n (%)
Total number of deaths	XX (XX.X)
Deaths during treatment period	XX (XX.X)
Deaths during rollover study	XX (XX.X)

N: the number of patients in the Treated set (TS). n: the number of patients who died. Percentages are calculated as $(100 \times n/N)$.

Path to the program code, date and time of output

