Abnormal NCS	XX (XX.X)
Abnormal CS	XX (XX.X)
...	
...	...

N: the number of patients in the Treated set (TS). n' - the number of valid observations.

n: the number of patients within a specific category. Percentages are based on the corresponding number of valid observations.

ML39355_STATISTICAL ANALYSIS PLAN_Final 2.0_17 June 2020

Path to the program code, date and time of output

Data extracted: DD.MM.YYYY

<The following assessments will be presented: Screening, Day 1, Baseline, Week 2, Week 4, Week 8, Week 16, Week 20, Week 26 Day 1, Week 26 Day 2, Follow-up visit, Week 39, Week 52>

ML39355_STATISTICAL ANALYSIS PLAN_Final 2.0_16 June 2020

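### SAP Table 3.14 divides rollover deaths by all treated patients, while SAP 9.2 and Table 3.10.2 count only patients who continued into the rollover

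*SAP*

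**What the plan says.** The shell for SAP Table 3.14 has three rows: all deaths, deaths in the treatment period, and "Deaths during rollover study". It has a single column with a single N. The note reads "N: the number of patients in the Treated set (TS). n: the number of patients who died", and the percentage in every row is 100 × n/N. The text of SAP 9.2 promises only a count: "Number of patients who died will be tabulated".

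For adverse events the SAP sets the population by period. SAP 9.2 runs the rollover period from the first rollover dose to 28 days after the last, and names its population as "Treated Set, patient continuing in the rollover study". The list of tables follows this, for example "Table 3.3.2 Treatment-emergent adverse events during rollover study (TS, patients continuing in the rollover study". Table 3.10.2, treatment-emergent events leading to death during the rollover, has the population line "Treated set (TS, patients continuing in the rollover study".

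Entry to the rollover is restricted. Under Protocol 3.1 and SAP 4.1 it is open to patients who get to Week 26 and have complied with treatment, and who then continue on commercial pirfenidone.

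**The concern.** A patient who died, withdrew or was non-compliant before Week 26 cannot have a rollover death, yet stays in the denominator of the rollover row. A reader will naturally take that percentage as the mortality of patients who continued treatment, and on that reading it is too low.

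The report would also disagree with itself. Protocol 5.3.5.7 requires every death in the reporting period to go on the adverse event form, and Table 3.10.2 counts events whose outcome is death. The two tables should therefore count largely the same rollover deaths but show them with different percentages. An unexplained discrepancy over mortality is worth avoiding, even in a descriptive study.

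**Working it through.** **Inputs from the documents.**
- N: about 60 treated. The SAP's sample size reproduces: 0.601 × 0.399 × (1.96/0.125)² = 0.2398 × 245.86 = 58.96, which the plan takes to 60.
- Table 3.14 percentage: 100 × n/N for every row, with N the Treated set.
- Table 3.10.2 population: Treated-set patients continuing in the rollover. The SAP gives only the title and population line for this table and adapts the notes from Table 3.3.1. I take the population line as fixing its N.

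**Inputs not in the documents.** The number entering the rollover (R) and the number of rollover deaths (d). The shells show placeholders only, so there is no planned percentage to reproduce. I assume d = 2 and let R run from 60 down to 20.

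**Formulas.**
- Table 3.14 prints 100 × d/N.
- The risk among those who can have the event is 100 × d/R.
- The ratio of the first to the second is R/N, whatever the value of d.

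**Results for N = 60, d = 2.** Table 3.14 prints 2/60 = 3.3% throughout.

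| R | 100 × d/R | R/N |
|---|---|---|
| 60 | 3.3% | 1.00 |
| 50 | 4.0% | 0.83 |
| 40 | 5.0% | 0.67 |
| 30 | 6.7% | 0.50 |
| 20 | 10.0% | 0.33 |

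The two figures agree only if every treated patient enters the rollover. At R = 40 the same two deaths could stand as 3.3% in Table 3.14 and 5.0% in Table 3.10.2.

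**The case against.** The best defence is that the Treated set is a legitimate and disclosed basis. SAP section 7 treats a patient as at risk for adverse events if that patient is in the Treated set. The shell states N and the formula. A common N lets the two period percentages add to the total. On that basis 3.3% is a valid quantity: the share of all treated patients who died during the rollover period. A rollover-based percentage for fatal events is already planned in Table 3.10.2, and Table 1.1 prints the number continuing, so a careful reader could recompute the figure.

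Much of this stands. The row is not an arithmetic error, and nothing is hidden. Two things remain. The general at-risk rule does not settle the matter, because SAP 9.2 narrows the population for the rollover period and all the rollover adverse event tables follow it; Table 3.14 is the exception, and no text explains why. And the gain in additivity is small, since the counts add up whichever denominator is printed.

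**Conclusion.** The point holds for one row. As a rollover-period risk, the percentage in the rollover row of Table 3.14 is too low by the factor R/N, and it departs from the SAP's own convention for that period. The direction is certain whenever R is below N. The size is not: it depends on an uptake that the documents do not give, and it vanishes at full uptake. The primary endpoint and the sample size are untouched.

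A reader might infer two stronger things that the documents do not support.

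- *That Table 3.14 as a whole has the wrong denominator.* It does not. The Treated set is right for total deaths and for deaths in the treatment period.
- *That Table 3.27 (physical examinations) has the mirror-image error and prints percentages that are too high.* After Screening, SAP 9.5 says "At subsequent visits, only limited, symptom-directed physical examinations should be performed", and the shell says "Percentages are based on the corresponding number of valid observations". But non-missing data are the SAP's default basis for categorical variables (section 7), and the number of observations is printed at each visit. The normal and two abnormal categories sum to 100% of those observations, so they cannot all be too high. Only the abnormal rows could be, and only if every unexamined body system is taken as normal, which no text says. With an assumed 60 attending and 5 abnormal, the shell would print 5/30 = 16.7% with 30 examined, against 5/60 = 8.3% under that unstated assumption. Dividing by attendance would build the assumption in. What remains is a caution on comparability: later percentages come from examinations prompted by symptoms and should not be read against the complete examination at Screening.

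**What to change.** In Table 3.14, give the rollover row its own footnoted denominator: Treated-set patients who took at least one dose in the rollover. Keep the Treated set for the total and treatment-period rows. The SAP already has a model for this, since Table 3.15 uses two footnoted denominators in one table. The change is one shell edit with no new data, because Table 1.1 already reports the number continuing. The small cost is that the row percentages no longer add to the total, although the counts still do.

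Optionally, add a footnote to Table 3.27 saying that examinations after Screening are symptom-directed, so percentages of those examined are not comparable with Screening. Its denominator need not change.

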4.5.13.6 Weeks 12 (\pm 2 Days)

The following procedures will be performed at Week 12:

- Directed history (including review of AEs/SAEs, concomitant medications, oxygen use, hospitalizations, dosing)
- EQ5D questionnaire (should be performed before any other non-PRO assessments)

Pirfenidone—F. Hoffmann-La Roche Ltd

- Physical examination, vital signs, and weight
- Clinical laboratory assessments, including hematology, serum chemistries, and pregnancy test for women of childbearing capacity
- Spirometry (FVC)
- 6MWT and Borg Scale
- Review patient's diary

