6.6. Multiple Testing

No adjustment for multiplicity is planned.

7. Summary of Study Data

Demographic and other baseline characteristics, efficacy and safety data will be summarized by time point of assessment and listed.

Default Summary Statistics

The default summary statistics for quantitative and ordinal variables will be the number of observations (n), mean, standard deviation (SD), median, minimum (Min) and maximum (Max).

Default Frequency Tabulations

For qualitative variables, the number and percentage (n, %) of patients with non-missing data per category and total number of patients with non-missing data where applicable (n') will be the default summary presentation.

For AEs and medical history, however, the denominator for the percentage calculation will be the number of patients at risk. A patient will be considered at risk if the patient is in the Treated set.

⁵ This section is based on the section 6.6 “Interim analysis” of clinical study Protocol.

ML39355_STATISTICAL ANALYSIS PLAN_Final 2.0_17 June 2020

The number of decimals for each descriptive statistic will be determined by the following rules:

- mean, median: +1 decimal symbols compared to the analysed variable values;
- standard deviation: +2 decimal symbols compared to the analysed variable values;
- minimum and maximum values: the same as for the analysed variable values;
- percentages will be rounded to one decimal symbol;
- confidence intervals will be presented with accuracy of the estimated value.

The maximum number of decimal places in the statistical report is four. If some descriptive statistic has more than four decimal places after above mentioned rules application, this value will be rounded to four decimal places.

Statistical Tests and Common Calculations

Unless otherwise specified in the description of the analyses, the following arrangements will be applied:

- 95% two-sided confidence intervals (CI);
- [if appropriate] CIs for mean values will be calculated based on normal distribution (SAS procedure UNIVARIATE with CIBASIC option);
- [if appropriate] CIs for proportions will be computed using the exact (Clopper-Pearson) method.
- Type I error values (p-values) will be rounded to four decimal symbols.

For descriptive statistics and analysis, the following rules will be applied:

- “<XX” results (e.g. below the limit of quantification, BLQ) will be replaced by the “XX/2” values;

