9.4. Clinical Laboratory Evaluations

eCRF form: “HEMATOLOGY”, “SERUM CHEMISTRY”.

Clinical laboratory evaluations as scheduled in the Table 1 include the following parameters:

- hematology (plasma): white blood cells (WBC) count, red blood cells (RBC) count, hemoglobin, hematocrit, platelet count, (relative) differential WBC count (neutrophils, eosinophils, basophils, monocytes, lymphocytes);
- blood chemistry panel (serum or plasma): albumin, alkaline phosphatase (AP), ALT, AST, direct bilirubin, total bilirubin, total protein, cholesterol, creatine kinase (CK), creatinine, triglycerides, gamma-glutamyl transferase (GGT), glucose, lactic dehydrogenase (LDH), calcium, phosphorus, magnesium, potassium, sodium, urea nitrogen, uric acid;

Creatinine clearance should be assessed at the Screening for eligibility confirmation using the following formula by Cockcroft-Gault (Cockcroft DW et al, 1976):

For serum creatinine concentration in mg/dL:

ML39355_STATISTICAL ANALYSIS PLAN_Final 2.0_17 June 2020

$$\text{CrCl (mL/min)} = (140 - \text{age (years)}) \times \text{weight (kg)} \times 1.0 / 72 \times \text{serum creatinine (mg/dL)}$$

For serum creatinine concentration in $\mu\text{mol/L}$:

$$\text{CrCl (mL/min)} = (140 - \text{age (years)}) \times \text{weight (kg)} \times 1.0 / 0.81 \times \text{serum creatinine } (\mu\text{mol/L})$$

For laboratory parameters the following tables will be presented according to section 7:

- descriptive statistics of measured values and changes from baseline (including creatinine clearance);
- shift tables based on comparison with normal range (Lower/Normal/Higher);
- frequency tables for Out of range: No/Yes clinically significant (Yes CS) / Yes non-clinically significant (Yes NCS) for laboratory parameters.

All laboratory data will be listed.

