Data extracted: DD.MM.YYYY

ML39355_STATISTICAL ANALYSIS PLAN_Final 2.0_17 June 2020
Pregnancies

F. Hoffmann-La Roche Ltd
 ML39355
Table 3.15 Urine pregnancy test
 Treated set (TS)
 Page X of X

	Total (N = XX) n (%)
Screening	
n'	XX
Done [1]	XX (XX.X)
Negative [2]	XX (XX.X)
Positive [2]	XX (XX.X)
Not Done [1]	XX (XX.X)
Male subject [1]	XX (XX.X)
Female subject with no childbearing potential [1]	XX (XX.X)
Other [1]	XX (XX.X)
Day 1	
n'	XX
Done [1]	XX (XX.X)
Negative [2]	XX (XX.X)
Positive [2]	XX (XX.X)
Not Done [1]	XX (XX.X)
Male subject [1]	XX (XX.X)
Female subject with no childbearing potential [1]	XX (XX.X)
Other [1]	XX (XX.X)
...	
...	...

N: the number of women of childbearing potential in the TS. n' - the number of valid observations.

n: the number of patients within a specific category.

[1] Percentages are based on the corresponding number of valid observations.

[2] Percentages are based on the number of patients for whom the pregnancy test was performed.

Path to the program code, date and time of output

Data extracted: DD.MM.YYYY

<The following Urine pregnancy test assessments will be presented: Screening, Day 1, Week 4, Week 8, Week 12, Week 20, Week 26 Day 2>

ML39355_STATISTICAL ANALYSIS PLAN_Final 2.0_17 June 2020
Laboratory tests

 F. Hoffmann-La Roche Ltd
 ML39355

Table 3.16 Hematology. Descriptive statistics

Treated set (TS)

Page X of X

Parameter: XXXXXXXXXXXXXXXXXXXX, <units>

	Total (N = XX)	Change from the baseline
Screening		
n	XX	
Mean	XX.X	
SD	XX.XX	
Median	XX.X	
Min	XX	
Max	XX	
Day 1		
n	XX	
Mean	XX.X	
SD	XX.XX	
Median	XX.X	
Min	XX	
Max	XX	
Baseline		
n	XX	
Mean	XX.X	
SD	XX.XX	
Median	XX.X	
Min	XX	
Max	XX	
Week 2		
n	XX	XX
Mean	XX.X	XX.X
SD	XX.XX	XX.XX
Median	XX.X	XX.X
Min	XX	XX
Max	XX	XX

ML39355_STATISTICAL ANALYSIS PLAN_Final 2.0_17 June 2020

...

...

...

N: the number of patients in the Treated set (TS).
n: the number of valid measurements.

The baseline value for a variable is defined as the last non-missing value collected before the first study drug administration.
<The following assessments will be presented: Screening, Day 1, Baseline, Week 2, Week 4, Week 8, Week 16, Week 20, Week 26 Day 2, Follow-up visit, Week 39, Week 52>
<The following parameters will be presented: Leukocytes ($10^9/L$), Erythrocytes ($10^{12}/L$), Hemoglobin (g/L), Hematocrit (L/L), Platelets ($10^9/L$), Neutrophils/Leukocytes (%), Eosinophils/Leukocytes (%), Basophils/Leukocytes (%), Monocytes/Leukocytes (%), Lymphocytes/Leukocytes (%).>

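### Ten SAP safety tables leave out Week 12, a visit at which the protocol collects laboratory tests, vital signs, weight and physical examination

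*SAP*

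**What the plan says.** **Data collection.** Protocol 4.5.13.6 lists for the Week 12 visit "Clinical laboratory assessments, including hematology, serum chemistries, and pregnancy test for women of childbearing capacity" and "Physical examination, vital signs, and weight". Protocol Appendix 1 marks the same assessments at Week 12. The SAP also treats Week 12 as a visit: section 7 gives it a window (study days 76 to 86), and Table 1.4 counts attendance at it.

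**Reporting rules.** Protocol 6.5 asks for descriptive statistics of laboratory variables and vital signs at every measured time point, and for laboratory shift tables at every time point. SAP section 7 sets the general rule that "efficacy and safety data will be summarized by time point of assessment and listed". SAP 9.4 refers to it: "For laboratory parameters the following tables will be presented according to section 7". SAP 9.5 does so for weight ("body weight (kg) and body height (cm) results will be presented in accordance with section 7"). For vital signs and physical examination, SAP 9.5 also points to the visit schedule: "Vital signs results will be presented by visit of assessment as scheduled in the Table 1" and "Physical examination results as scheduled in the Table 1 will be presented in accordance with section 7 by visit of assessment".

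**Table shells.** The note under Table 3.16 lists "Screening, Day 1, Baseline, Week 2, Week 4, Week 8, Week 16, Week 20, Week 26 Day 2, Follow-up visit", followed by Weeks 39 and 52. Six further shells have lists that also pass from Week 8 to Week 16.

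**The concern.** The rules in the text and the visit lists in the shells give the programmer two different instructions. If the shells are followed, the by-visit tables contain no Week 12 means, shifts from baseline or out-of-range counts. That leaves eight weeks of treatment, from Week 8 to Week 16, with no summarized visit. Change from baseline in laboratory parameters is a named safety endpoint (SAP 3.2.4). Protocol 5.1.1.3 and 5.1.1.5 name transaminase elevation and weight loss as known risks of the drug. SAP section 14 declares no departure from the protocol, so nothing marks the omission as deliberate.

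**Working it through.** The plan has no figure to reproduce here. The check compares each shell's visit list with the scheduled visits in Protocol 4.5.13.5 to 4.5.13.10.

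| Shell | Content | Scheduled visit missing | Rule it conflicts with |
|---|---|---|---|
| 3.16 | Hematology, descriptive | Week 12 | Protocol 6.5 |
| 3.17 | Chemistry, descriptive (modelled on 3.16) | Week 12 | Protocol 6.5 |
| 3.18 | Hematology, shift | Week 12 | Protocol 6.5 |
| 3.19 | Chemistry, shift (modelled on 3.18) | Week 12 | Protocol 6.5 |
| 3.20 | Hematology, out of range | Week 12 | SAP 7 through 9.4 |
| 3.21 | Chemistry, out of range (modelled on 3.20) | Week 12 | SAP 7 through 9.4 |
| 3.22 | Vital signs, descriptive | Week 12 | Protocol 6.5 |
| 3.23 | Vital signs, out of range | Week 12 | SAP 7 and 9.5 |
| 3.24 | Weight | Week 12 | SAP 7 through 9.5 |
| 3.25, 3.26 | ECG | None (no ECG at Week 12) | None |
| 3.27 | Physical examination | Week 12 | SAP 7 and 9.5 |

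**Counts.** There are 12 shells from 3.16 to 3.27. Seven explicit lists plus three inherited ones give 10 affected. Five of these (3.16 to 3.19 and 3.22) conflict with Protocol 6.5. For the other five, Protocol 6.5 states no time points, so the conflict is with the SAP's own text.

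**Share of post-baseline assessments left out.**

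- Laboratory and weight, Weeks 2, 4, 8, 12, 16, 20 and 26 (second day): 7 visits, so 1/7 = 14.3%.
- Vital signs and physical examination add the first Week 26 day: 8 assessments, so 1/8 = 12.5%.
- Adding rollover Weeks 39 and 52: laboratory 7 + 2 = 9, so 1/9 = 11.1%; vital signs and physical examination 8 + 2 = 10, so 1/10 = 10.0%. Weight is not scheduled at those visits and stays at 1/7.

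These figures do not count the follow-up visit 14 to 28 days after the last dose. Counting it as well gives laboratory 1/10 = 10.0%, vital signs and physical examination 1/11 = 9.1%, and weight 1/8 = 12.5%.

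**Slip or choice?** Week 12 is the only scheduled visit missing from each of the seven lists. Pregnancy-test Table 3.15, which stands directly before Table 3.16, keeps Week 12, as do the FVC, 6MWT and EQ-5D shells. This looks like one list copied with an omission, not a decision to drop the visit.

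**The case against.** The best case on the other side is that little depends on this.

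- **Consequence.** Week 12 values remain in Listings 30, 31, 32 and 34, and abnormalities that qualify as adverse events reach the adverse-event tables. The laboratory endpoint names no visit. Physical examinations after screening are limited and symptom-directed. All of this stands, and it keeps the point minor.
- **Force of the SAP rule.** SAP section 7 prescribes a layout by time point without saying that every time point must appear, so an explicit visit list could be read as refining it. This has some weight for Table 3.24 (weight), where SAP 9.5 only refers back to section 7. It has less for vital signs and physical examination, where SAP 9.5 also invokes the visit schedule, and none for the five tables under Protocol 6.5.
- **SAP section 14.** Its statement concerns analysis methods, and a visit list in a shell is arguably not a method. That is fair, but the conflict does not depend on section 14.
- **Schedule source.** The relevant rows of SAP Table 1 are not in the text available for review. The SAP cites a protocol dated 01.02.2019, while the one reviewed is dated 09-Jun-2018. The Week 12 entries are therefore read from the reviewed protocol. The SAP's own Week 12 window and attendance count make a dropped visit unlikely.

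**Conclusion.** The inconsistency is real. Seven visit lists omit Week 12 and three more tables inherit the gap, so 10 of 12 shells disagree with the protocol or with the SAP's own text. The loss is one scheduled assessment per affected table. It is confined to summary tables and does not touch data collection or any inference. The conclusion assumes that the protocol version cited by the SAP keeps the Week 12 safety assessments. This is a low-priority correction, but worth making, because the shells as written drop a scheduled visit from the tables that report a named safety endpoint.

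**What to change.** Insert Week 12 between Week 8 and Week 16 in the visit lists of Tables 3.16, 3.18, 3.20, 3.22, 3.23, 3.24 and 3.27. Tables 3.17, 3.19 and 3.21 then inherit it. Leave ECG Tables 3.25 and 3.26 and pregnancy-test Table 3.15 unchanged. Before editing, check the Week 12 column of SAP Table 1 in the signed document. The cost is a text edit to seven shell notes; the data are already collected and listed.
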